## 9.2 Setting

### 9.2.1 Subject Participation and Identification

Individuals vaccinated with Q/LAIV and controls will be identified for inclusion in this study via the Kaiser Immunization Tracking System (KITS) database. Immunizations of KP

members are recorded in this database as part of routine care. Because each recipient has a unique medical record number assigned once enrolled in the KP Health Care Plan and because administration records of all vaccinees are entered in the KITS database, the study population can be assembled from the KITS system on an ongoing basis.

The lot number of administered vaccine is entered in the KITS immunization database for each vaccinee.

### 9.2.2 Inclusion Criteria

Subjects must meet *all* of the following criteria:

- 1) Age 2 through 49 years (prior to 50th birthday) at the time of vaccination (or index date for unvaccinated controls)
- 2) Membership in the KP Health Care Plan for at least 12 months prior to vaccination/index date
- 3) Continuous enrollment in the KP Health Care Plan through 6 months following vaccination/index date.

There are no exclusion criteria. Subjects with any high-risk underlying medical condition as defined by ICD-9-CM codes or successor ([Annex 3](#)) will be analyzed separately.

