## 8 Research Question and Objectives

The objective of this study is to assess the safety of Q/LAIV vaccination in children and adults 2 through 49 years of age within 180 days after vaccination: incidence rates of adverse events of interest during periods at risk after Q/LAIV vaccination will be compared to incidence rates during reference periods later in the follow-up (within-cohort analysis) and to incidence rates in controls (matched unvaccinated subjects and matched IIV recipients).

Since there are no identified safety concerns with Q/LAIV, this postmarketing safety assessment is hypothesis generating.

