- 1) Inactivated influenza vaccine recipient controls who received the current IIV formulation (trivalent or quadrivalent) but not Q/LAIV for the season at a Kaiser health maintenance organization (HMO) during the same month that the reference Q/LAIV recipient was vaccinated will be identified and matched based on age (year) and medical center relative to concurrent reference Q/LAIV recipients, using frequency matching. For children 2 to 4 years of age, matching by age will be based on calendar quarter of birth rather than year. Factors such as gender and prior health care utilization level will be included as covariates in the proposed Cox proportional hazards model.
- 2) Unvaccinated controls who did not receive any influenza vaccine for the season will be identified and matched based on age (year) and medical center relative to concurrent reference Q/LAIV recipients using frequency matching. For children 2 to 4 years of age, matching by age will be based on calendar quarter of birth rather than year. Factors such as gender and prior health care utilization level will be included as covariates in the proposed Cox proportional hazards model. Unvaccinated controls will be followed from the date of vaccination of the reference Q/LAIV recipient (the index date).

Health care utilization levels will be defined as “high” ( $\geq 2$  visits to a Kaiser HMO within the 6 months prior to the date of vaccination of the reference Q/LAIV vaccinee) or “low” ( $\leq 1$  visit).

The study is expected to begin in the fall of 2013 following the launch of Q/LAIV and to be completed in a single influenza season. However, if fewer than 10,000 Q/LAIV recipients 2 through 8 years of age are identified following the 2013-2014 influenza season, the study will be continued for additional seasons until enrollment of 10,000 Q/LAIV recipients is completed. A detailed description of safety follow-up is described in Section 11. Data will be collected on subjects for 180 days following vaccination (or the index date for unvaccinated controls).

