**Table 9.3-1 Summary of Planned Analyses**

Event of Interest	Period at Risk After Vaccination	Reference Period
Hypersensitivity MAEs a Seizures/convulsions MAEs a	0-3 days c	7-9 days d
Lower respiratory MAEs Wheezing MAEs Guillain-Barré syndrome MAEs a Bell's palsy MAEs a Encephalitis MAEs a Neuritis MAEs a Vasculitis MAEs a Any hospitalization Respiratory hospitalization b	1-42 days c (1-14 days and 15-42 days)	43-84 days
Narcolepsy/cataplexy MAEs a	1-180 days c	NA

MAE = medically attended event; NA = not applicable

a Narratives of each case will be included in the final clinical study report.

b A respiratory hospitalization will be defined by the ICD-9-CM codes sets for lower respiratory MAEs and wheezing MAEs.

c It is not possible to detect from clinical databases whether an event occurring on the day of vaccination began prior to or after administration of vaccine, although events of hypersensitivity or seizures/convulsions may occur just subsequent to vaccination but are unlikely to be recorded on the same day prior to vaccination. As a result, the period at risk after vaccination for events of hypersensitivity and seizures/convulsions begins on the day of vaccination (Day 0), and the period at risk after vaccination for all other events of interest begins 1 day after vaccination (Day 1).

d The reference period for the period at risk for 0 to 3 days was defined from 7 to 9 days to take into account cyclical variations that may occur during the same days of the week.

An MAE is defined as a coded medical diagnosis made by a health care provider and associated with a medical encounter (ie, visit to a medical clinic or emergency department, or a hospital admission). One or more MAEs could be assigned for a single encounter.

For MAEs of Guillain-Barre syndrome, Bell's palsy, encephalitis, neuritis, vasculitis, and narcolepsy/cataplexy, events will only be counted if the subject does not have a prior record of the event in the 12 months prior to vaccination (or index date for unvaccinated controls).

In addition, listings of any hospitalization within 180 days, any deaths throughout the entire study period, and exposed pregnancies throughout the entire study period will be provided.

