#### 9.7.4 Multivariable Analysis

One of the primary challenges with performing safety assessment in this setting is that the background rates of many outcomes, such as respiratory events, change over time during the period of vaccination and follow-up. These changes in background rates are due to factors such as patterns in circulation of a variety of respiratory viruses and changes in exposure due to behavior influences such as the school year and holidays.

Controlling for seasonal changes in background rates that are dependent upon calendar time is important to minimize the potential seasonal bias and ensure that the effect of Q/LAIV on the rate of these events from a safety perspective, if any, can be accurately estimated.

The counting-process style of input for the Cox proportional hazards model can accomplish this by allowing the use of calendar time as the structure for defining the observation intervals ([Andersen and Gill, 1982](#)). Rows of observations for each subject will be generally structured as:

*pid, caldtst, caldtsp, event*

where *pid* is the subject identifier, *caldtst* is the calendar date of the beginning of the observation period, *caldtsp* is the calendar date of the end of the observation period, *event* is 1 if an event occurred at the end of the observation period, and 0 if an event did not occur, indicating censoring.

101,	11Oct2013,	22Nov2013,	0
102,	15Oct2013,	02Nov2013,	1

indicates that participant 101 was under observation from October 11 through November 22 and did not experience an event and was censored on November 22. Participant 102 was under observation from October 15 and experienced an event on November 02. Although not shown in this example, the values of main effects and covariates would also be included in each row.

This method controls for the effect of seasonal and other calendar time differences on background event rates because, when each component of the Cox partial likelihood is calculated at each event, the risk set includes only subjects who were under observation during the same calendar time period.

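### Eligibility depends on plan enrollment for 6 months after vaccination, with no exception for death; read literally, this conflicts with the promised listing of deaths and can remove fatal cases

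*Protocol*

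**What the plan says.** Protocol Section 9.2.2 has three inclusion criteria, all of which must be met. The third is "Continuous enrollment in the KP Health Care Plan through 6 months following vaccination/index date". The Population part of the abstract (Section 4) repeats it. The section adds "There are no exclusion criteria", and no exception for death or disenrollment appears anywhere. The criterion applies to Q/LAIV recipients and to both control groups.

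Four other parts of the protocol bear on it:

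- **Outputs.** The text under Table 9.3-1 promises "listings of any hospitalization within 180 days, any deaths throughout the entire study period". Footnote a promises a narrative for every case of several events, including Guillain-Barré syndrome and encephalitis.
- **Time frame.** Section 8 sets the safety objective over the 180 days after vaccination, and Section 9.1 limits data collection to the same period.
- **Methods.** Section 9.7.3 reports rates per 1,000 person-years. Section 9.7.4 uses start/stop rows in a Cox model, with the event indicator set to "0 if an event did not occur, indicating censoring".
- **Limitations.** Section 9.9 discusses indication bias, coding validity and very rare events. It does not mention selection on survival or enrollment after vaccination.

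**The concern.** An eligibility rule for a safety cohort should be decidable at the index date. This one depends on what happens afterwards, and one way to fail it is to die. The subjects it can remove include those with the gravest outcomes, in a study that implements a postmarketing commitment to the US FDA.

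Two things are at stake. A death listing that is empty for the first 6 months would look reassuring but carry no information if subjects who died had been made ineligible. Also, a fatal case of an event in Table 9.3-1 would leave the numerator, the denominator and the narratives together. A subject admitted on day 10 who dies on day 30 is an example.

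The SAE route in Section 11.1.2 does not fill the gap. It covers only events that an investigator happens to learn of and considers possibly related to Q/LAIV.

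**Working it through.** **1. The plan's own figures.** The protocol gives no number for deaths or turnover, so there is none to reproduce on this exact point. Its size statements do reproduce:

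- Power with 10,000 per group (1:1 is an assumption), 1.0% versus 1.5%, two-sided 0.05: (0.005 − 1.96 × 0.001571) / 0.001571 = 1.22, or 88.9%, against a stated 90% or so.
- Rule-out rate: −ln(0.05) / 10,000 = 0.02996%, against a stated 0.03%.

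Neither depends on criterion 3. However, the rule-out statement presumes that every occurrence among vaccinees is counted. A zero produced by an eligibility rule rules nothing out.

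**2. Enrollment window against data window.** Six calendar months from 1 September 2013, 15 October 2013 and 1 January 2014 are 181, 182 and 181 days. Each exceeds 180, so the enrollment condition spans the whole data-collection period. Plan membership ends at death. On the literal wording, a subject who dies on any of days 0-180 fails criterion 3, and the number of eligible subjects who die in the window is 0.

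**3. Illustrative number of deaths.** The mortality range is assumed: 0.1 to 1.0 per 1,000 person-years.

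- Person-time for 80,000 recipients (Section 9.5): 80,000 × 180 / 365.25 ≈ 39,400 person-years.
- Deaths: 39,400 × 0.0001 ≈ 4, up to 39,400 × 0.001 ≈ 39.
- For 10,000 children: about 4,930 person-years, or about 0.5 to 5 deaths.

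**4. Subjects who leave.** Someone who leaves on day 150 has complete data for days 0-3, 7-9, 1-42 and 43-84, but the rule discards all of it. Only the narcolepsy window (days 1-180) and the 180-day hospitalization listing are incomplete for that person.

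**5. Effect on relative risks.** Let f1 and f0 be the shares of cases lost through death or departure in the exposed group (or risk period) and in the comparison group (or reference period). If removing these cases hardly changes the person-time, then observed RR = true RR × (1 − f1) / (1 − f0). With a true RR of 1.5 and assumed shares:

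| f1 | f0 | Observed RR |
|---|---|---|
| 10% | 10% | 1.5 × 0.90/0.90 = 1.50 |
| 10% | 5% | 1.5 × 0.90/0.95 = 1.42 |
| 20% | 10% | 1.5 × 0.80/0.90 = 1.33 |
| 30% | 10% | 1.5 × 0.70/0.90 = 1.17 |

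Equal loss leaves the ratio unchanged and lowers only the counts and rates of the affected events. Unequal loss in the direction shown pulls a real increase toward 1; the reverse inequality would inflate it.

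**6. Whether the methods need the rule.** Person-year denominators and start/stop rows both accept partial follow-up. Section 9.4 says HMO membership is among the source data, so an end-of-enrollment date should be obtainable.

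**The case against.** The strongest reply is that the protocol never says death counts as failing the enrollment criterion. The promise to list deaths, together with death as the first SAE criterion in Section 11.1.1, suggests that the sponsor meant to keep subjects who die. That is fair as a reading of intent. A reader might infer that the protocol definitely excludes every death within 6 months; that holds only on the literal wording. The wording offers no other rule, though, so whoever builds the cohort must choose between two conflicting sections.

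A reader might also infer that all event rates are biased downward. The documents do not support that. Administrative leavers drop out of numerator and denominator together, and nothing shows that they have more events than those who stay. In the within-cohort analysis the same recipients supply risk and reference time, so disenrollment unrelated to events does not bias that contrast. Nor does any section show that loss differs between Q/LAIV, inactivated-vaccine and unvaccinated members.

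Criterion 3 also has an evident purpose. Events come only from the plan's databases and may be missed after someone leaves, and some outputs run to 180 days. A cohort with complete follow-up is less efficient rather than invalid as regards administrative leavers. Finally, death is listed but not compared, the study is described as hypothesis generating, and most events of interest are probably non-fatal at these ages. The effect on most planned hazard ratios is therefore likely to be small.

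What remains is the treatment of death and of events that lead to departure.

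**Conclusion.** The point holds in this form. Criterion 3 selects on a post-exposure outcome. As written, it conflicts with the promised death listing, can remove fatal cases from counts and narratives, and is not disclosed as a limitation.

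Its consequences differ by type of loss:

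- **Death, or departure caused by an event:** counts and rates are understated. Hazard ratios are biased only if the loss differs between the compared groups or periods.
- **Unrelated disenrollment:** precision is lost, and no bias is shown.

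The size cannot be fixed from the protocol. The 4-39 deaths rest on assumed mortality, and the expected 80,000 may already be a count of eligible subjects. For the same reason, no number of lost leavers can be derived. The altered relative risks show how the mechanism works and are not forecasts. The sample-size statements are unaffected.

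This is not detail that could be left to an analysis plan: censoring rules cannot restore subjects whom the protocol makes ineligible.

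**What to change.** In Sections 4 and 9.2.2, base eligibility on age and the 12-month prior membership only. Follow each subject from vaccination or index date to the earliest of event, end of window, disenrollment or death, and censor there in both the person-time rates and the Cox models. List all deaths and report disenrollment by group. Keep the cohort continuously enrolled for 6 months as a sensitivity analysis.

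If the sponsor prefers to keep criterion 3 for administrative leavers, the minimum change is a sentence stating that subjects who die during follow-up remain eligible, plus a line in Section 9.9 acknowledging the selection.

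The cost is a short amendment and a censoring date from membership data already among the sources. The downside is unequal follow-up, which the planned methods handle, and a somewhat smaller share of subjects with full 180-day observation for narcolepsy.

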## 9.7 Data Analysis

### 9.7.1 Analysis Populations

The populations to be assessed are all Q/LAIV recipients and the nonrandomized control groups (unvaccinated subjects, and IIV recipients) as described in Section 9.1.

Analyses will also be performed by age group (2 to 4 years, 5 to 8 years, 9 to 17 years, 18 to 49 years) and setting (clinic, hospital, emergency department).

Q/LAIV recipients with medical conditions that are a warning/precaution against the use of Q/LAIV (see Package Insert; [Annex 4](#)) will be analyzed separately. Subjects will be identified as having these conditions by using the International Classification of Diseases Clinical Modification (ICD-9-CM or successor) diagnosis codes as outlined by [Daley et al, 2004](#) (see [Annex 3](#)).

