#### **9.7.4.2 Analyses Versus Matched Controls**

Analyses will be conducted to see if the incidence of safety outcomes is higher among Q/LAIV recipients compared to matched controls (unvaccinated or IIV) within post-vaccination “risk” periods (eg, 0 to 3 days, 1 to 42 days, and 1 to 180 days post vaccination).

This will be accomplished in the Cox models by evaluating the main effect of “treatment group.” Covariates, stratification factors, and the calendar time structure will be incorporated to control for the effects of age, gender, level of health care utilization, and seasonal difference in background event rates.

The main effect variable “treatment group” will be coded as follows:

*Treatment (for unvaccinated control analysis)*: 1 = Q/LAIV, 0 = unvaccinated

*Treatment (for IIV control analysis)*: 1 = Q/LAIV, 0 = IIV

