**4 CONTRAINDICATIONS**

**4.1 Severe Allergic Reactions**

Do not administer FluMist Quadrivalent to persons who have had a severe allergic reaction (e.g., anaphylaxis) to any component of the vaccine [see Description (11)] including egg protein, gentamicin, gelatin, and arginine, or after a previous dose of any influenza vaccine.

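### Matched hypersensitivity comparison keeps controls whom the annexed label contraindicates for severe allergy, and names no adjustment for allergy history; taken alone this lowers the HR, by an amount the protocol cannot settle

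*Protocol*

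**What the plan says.** Table 9.3-1 lists hypersensitivity MAEs with a risk period of Days 0-3. Section 9.7.3 plans comparisons of the listed events with both control groups, and section 9.7.4.2 names the 0-3 day window for them.

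- **Eligibility (9.2.2):** "There are no exclusion criteria". This applies to every group.
- **Annexed label (Annex 4, 4.1):** "Do not administer FluMist Quadrivalent to persons who have had a severe allergic reaction (e.g., anaphylaxis) to any component of the vaccine", "including egg protein, gentamicin, gelatin, and arginine, or after a previous dose of any influenza vaccine".
- **Matching (9.1):** "Unvaccinated controls who did not receive any influenza vaccine for the season will be identified and matched based on age (year) and medical center". IIV controls are vaccinated in the same month and are likewise "matched based on age (year) and medical center relative to concurrent reference Q/LAIV recipients, using frequency matching".
- **Cox model (9.7.4.2):** covariates, strata and calendar time are used "to control for the effects of age, gender, level of health care utilization, and seasonal difference in background event rates".
- **Prior-event rule (below Table 9.3-1):** "For MAEs of Guillain-Barre syndrome, Bell's palsy, encephalitis, neuritis, vasculitis, and narcolepsy/cataplexy, events will only be counted if the subject does not have" a record of the event in the preceding 12 months. Hypersensitivity is not on that list.
- **Separate label-based analysis (9.7.1):** "Q/LAIV recipients with medical conditions that are a warning/precaution against the use of Q/LAIV". It covers recipients only, and warnings rather than contraindications.
- **Complementary analysis (9.9):** drops subjects with high-risk conditions. Annex 3, which defines them, has no allergy or anaphylaxis category.

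**The concern.** A past severe allergic reaction plausibly predicts a new hypersensitivity visit, and under the label it also steers people away from Q/LAIV. It can therefore confound exactly this outcome. If the label is followed, the Q/LAIV group holds fewer such people than the population from which controls are drawn. Unvaccinated controls may hold more than their share, since people who avoid influenza vaccine after a reaction end up there.

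That raises the comparator rate and pulls the HR down, which in a safety study is the direction that can mask harm. Section 9.7.3 declares significance in both directions from the adjusted HR, so the same pull could also produce a formally declared decrease in risk. None of the safeguards in the protocol addresses allergy history.

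**Working it through.** **The plan's own power figure.** Section 9.5 states about 90% power for RR 1.5 with 10,000 children and a comparison rate of 1 in 100. No control ratio is stated, so I assume 1:1, with two-sided alpha 0.05:

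z = [0.005 − 1.96·√(2 × 0.0125 × 0.9875/10,000)] / √[(0.015 × 0.985 + 0.01 × 0.99)/10,000] = (0.005 − 0.00308)/0.00157 = 1.22, giving power 88.9%.

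The same formula for 20,000 and 1 in 200 gives 88.7%. The stated figure reproduces for groups with the same background risk.

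**Bias model.** Let p be the excess prevalence of label-contraindicated allergy in controls over Q/LAIV recipients, and k the multiple by which it raises the rate of hypersensitivity MAEs. Then

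observed HR = true HR / [1 + p(k − 1)].

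The protocol gives neither p nor k. Every value below is an assumption.

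**Effect on the signal rule.** Further assumptions: 80,000 per group (the expected Q/LAIV total; control numbers are not stated) and r₀ = 1 event per 1,000 eligible persons over Days 0-3. Expected control events are e₀ = 80,000 × r₀ × [1 + p(k − 1)]; Q/LAIV events are e₁ = 80,000 × r₀ × true HR; SE(log HR) = √(1/e₀ + 1/e₁).

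Example with p = 1%, k = 10:
- True HR 1.5: e₀ = 87.2, e₁ = 120, SE = 0.141, log(1.5/1.09) = 0.319. Power = Φ(0.319/0.141 − 1.96) = 62%.
- True HR 1: e₁ = 80, SE = 0.155, log(1.09) = 0.086. Chance of declaring a decrease = Φ(0.086/0.155 − 1.96) = 8%.

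| p | k | Factor | True HR 1.5 seen as | Power for HR 1.5 | Decrease declared at true HR 1 |
|---|---|---|---|---|---|
| 0 | – | 1.000 | 1.50 | 80% | 2.5% |
| 0.1% | 5 | 0.996 | 1.49 | 80% | 2.7% |
| 0.1% | 10 | 0.991 | 1.49 | 79% | 2.9% |
| 0.5% | 10 | 0.957 | 1.43 | 72% | 5% |
| 1% | 10 | 0.917 | 1.38 | 62% | 8% |
| 2% | 10 | 0.847 | 1.27 | 42% | 19% |
| 1% | 20 | 0.840 | 1.26 | 39% | 21% |
| 2% | 20 | 0.725 | 1.09 | 9% | 59% |

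**Sensitivity to the event rate.** At 0.5 events per 1,000, power without bias is 51%, and it falls to between 43% (0.5%, k = 10) and 22% (1%, k = 20). At 0.3 per 1,000 it is only 34% before any bias, so scarcity of events then limits the comparison more than most of these scenarios do.

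**Under the plan's own scenario** (10,000 and 1 in 100), power goes from 88.9% to 88.4% (0.1%, k = 5), 72.7% (1%, k = 10) or 50.3% (2%, k = 10).

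**What would hide an HR of 1.5 entirely.** This needs p(k − 1) = 0.5, for example p = 1% with k = 51, or p = 5% with k = 11.

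**The case against.** A reader might infer that the matched hypersensitivity HR is biased below 1 and will hide a vaccine effect. The documents do not support that, for these reasons:

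- **Size.** The mechanism lowers the HR relative to its true value; whether the estimate falls below 1 depends on p, k and the true HR. The contraindication concerns severe reactions, and p is only their excess in controls. At 0.1% the effect is negligible.
- **Net direction against unvaccinated controls.** The window includes Day 0, when Q/LAIV recipients have a vaccination encounter and unvaccinated controls have only an assigned index date. That can push the HR up.
- **IIV controls.** They have just accepted an influenza vaccine, and the IIV label is not in the protocol. Nothing shows how many had a prior severe reaction.
- **Recipients.** Contraindicated people who received Q/LAIV are not excluded either, which narrows the gap.
- **Other evidence.** Hypersensitivity is also tested within the Q/LAIV cohort (Days 0-3 against 7-9), where control selection plays no part, and every case gets a narrative.
- **Disclosure and open wording.** Sections 9.1 and 9.9 admit residual differences, the study is hypothesis generating, and the covariates in 9.1 are given only as examples. An SAP could add allergy history, so unadjusted here means not named in the protocol.

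All of this limits the claim; none of it removes it. An opposing bias of unknown size is not a correction, narratives do not adjust an HR, and the general caveats come with remedies that do not reach allergy. The matched HRs still carry their own significance rule.

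**Conclusion.** The point holds in limited form. In the matched comparisons for hypersensitivity, label-contraindicated people remain eligible as controls and allergy history is not named anywhere as an exclusion, matching factor or covariate. Taken alone, this multiplies the HR by a factor below 1.

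The factor runs from 0.996 to 0.725 over assumed ranges of 0.1-2% excess prevalence and a hazard multiple of 5-20. These ranges are illustrative and do not come from the protocol. The power figures rest further on an assumed 1:1 ratio and assumed event rates. The net direction against unvaccinated controls is not established, and an excess in IIV controls is plausible but not documented. The within-cohort result is not touched. This is a cheap improvement to one outcome, not a flaw in the study as a whole.

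**What to change.** In section 9.7.4.2, for hypersensitivity MAEs against each control group:

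- Keep the planned HR.
- Add one pre-specified analysis that either adjusts for, or excludes from all groups, subjects with a coded severe allergic reaction, vaccine-component allergy or influenza-vaccine reaction before the vaccination or index date. Use at least the 12-month look-back that inclusion criterion 2 guarantees.
- Describe separately any Q/LAIV recipients with such a history, so that restriction does not drop them from view.

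In section 9.9, name this channelling, state that the within-cohort result has priority for hypersensitivity, and state that a significantly decreased risk against controls is not to be read as protective.

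The cost is one code list and one extra model per control group on data already held. Some bias will remain, because coded history over 12 months is incomplete and older reactions will be missed. If subjects are excluded, the added HR applies only to those without a coded history.
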